The primary aim of the proposed study is to evaluate the change in global CBF with ACZ, so the primary outcome is the change in global CBF after 24 weeks relative to pre-treatment baseline. Based on the preliminary data, we expect to see a 15% difference between the ACZ treatment and placebo groups on the improvement in global cerebral perfusion with standard deviation (SD) of 30%. We ran Monte Carlo simulations under a linear mixed effect model (same model as planned for analysis) and calculated a needed total sample size of n=50 to detect a group difference of 0.5 SD at the 24 weeks (phase 1) assuming a within-subject correlation of 0.5, a significance level of 0.05, and 90% power. We hypothesize a similar group difference in phase 2 (ACZ-ACZ group would not change between weeks 24 and 48 but delayed-start group would improve) and similar power to detect this effect. With 50 patients, for Aim 1.2, we will have 80% power to detect an average correlation as low as 0.39 between CBF and MD or FA. Considering a dropout rate of 18%, we need to recruit 60 participants. Aims 2 are mainly exploratory and parameters derived from this study will be used to help design future larger scale confirmatory studies.

All analyses will be intent-to-treat. To summarize the data, descriptive statistics will be used. Demographics and baseline characteristics at randomization will be summarized for each treatment arm. Generalized linear mixed models will be used to analyze all outcomes and will include treatment group and time, group-by-time interaction, and disease duration (stratifying variable) as covariates, and a random intercept to account for within-patient correlation.

For the primary outcome, we will focus on comparing the treatment groups in phase 1. A linear mixed model will be used to compare the estimated change in global CBF between baseline and week 24 in the ACZ and delayed-start groups. A secondary analysis will study ACZ treatment effect on CBF in different regions by treating regions as clusters in the linear mixed model. If normality of CBF outcome does not hold, an appropriate transformation or different outcome distribution will be used.

For the secondary endpoint at 48 weeks (phase 2), a similar mixed model will be used to compare changes in global CBF between weeks 24 and 48 weeks in the early-start and delayed-start groups. The model will include the same terms as for phase 1.

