Secondary outcomes considers repeated measures of MD or FA at different time in different regions. Linear mixed models will be used to evaluate changes in MD and FA from baseline (24 weeks for delayed-start) to 24 weeks (48 weeks for delayed-start) after ACZ therapy. These changes will be compared between regions with and without increased CBF (>15% difference from baseline). Terms in the model will be as for CBF with the addition of increased CBF (yes/no) for the region. Mixed models will also be used to compare MD and FA changes between white matter areas with and without lesions.

Logistic or linear mixed models will be used to evaluate change from baseline to after 24 week ACZ therapy (using phase 1 and phase 2 data) in the tertiary composite change outcome. Models will include the same terms as for analyses of the primary outcome. We will evaluate associations between changes in clinical outcomes and changes in CBF, CBV, and MTT by including each of these variables (one at a time) as a time-varying covariate.

As this trial uses a small sample size, we would not expect statistically significant treatment effects on clinical disability though this exploratory measure should be useful in power calculation for the anticipated larger, randomized clinical trial.

ETHICAL CONSIDERATIONS

Informed Consent

The informed consent form is a method of providing information regarding the trial to a prospective participant and allows for an informed decision about participation in the study. All participants (or their legally acceptable representative) must read, sign, and date a consent form before participating in the study, taking study drug, and/or undergoing any study-specific procedures. If a participant does not speak and read English, the consent materials will be translated into the Spanish.

The informed consent form will be updated or revised whenever important new safety information is available, whenever the protocol is amended, and/or whenever any new information becomes available that may affect a subject's participation in the trial.

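### The MD/FA analysis names no week 0–24 ACZ-versus-placebo contrast: its stated windows are each arm's own first 24 weeks on ACZ, and its named comparisons are not randomised

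*Combined protocol and SAP*

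**What the plan says.** All references are to the combined protocol and SAP.

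- **Objective.** Primary & Key Secondary Objective makes improved tissue integrity in a proportion of lesions, under long-term oral ACZ, the key secondary endpoint. DTI is one measure, to be correlated with CBF increases; lesion number, lesion volume and the T1/T2 ratio are others. The Stage 3 text in Rationale for Study Design expects the improvement to appear on diffusion tensor metrics.
- **MD/FA windows.** Section 11 evaluates "changes in MD and FA from baseline (24 weeks for delayed-start) to 24 weeks (48 weeks for delayed-start) after ACZ therapy". Under Study Visits and Procedures, Stage 3 Visit 5, the placebo arm moves to ACZ at week 24 and all patients then stay on ACZ.
- **MD/FA comparisons.** "These changes will be compared between regions with and without increased CBF (>15% difference from baseline"), and mixed models will also "compare MD and FA changes between white matter areas with and without lesions".
- **Model terms.** In general: "Generalized linear mixed models will be used to analyze all outcomes and will include treatment group and time, group-by-time interaction", plus disease duration and a random intercept. For MD/FA: "Terms in the model will be as for CBF with the addition of increased CBF (yes/no) for the region".
- **Contrast named for CBF.** The primary analysis will "compare the estimated change in global CBF between baseline and week 24 in the ACZ and delayed-start groups". No matching sentence exists for MD or FA.
- **MD/FA power.** The only statement is "80% power to detect an average correlation as low as 0.39 between CBF and MD or FA".

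**The concern.** Whether ACZ improves tissue integrity is a question about a drug effect, and Stage 3 randomises patients to ACZ or placebo for 24 weeks. The delayed-start arm's placebo period is the only concurrent control, yet it lies in neither MD/FA window. A change from the start to the end of 24 weeks on ACZ mixes any drug effect with whatever MD and FA would have done anyway. That could flatter the drug or hide a benefit.

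The two region comparisons do not supply the missing control. One sorts regions by CBF response, which is observed after randomisation; the other sorts them by lesion status. The pilot is meant to inform a larger randomised trial, and for that a between-arm estimate is the useful quantity.

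**Working it through.** **1. The plan's own MD/FA figure.** Inputs from section 11: n = 50, r = 0.39, power 80%, alpha 0.05 (two-sided assumed). Fisher z: n = ((1.960 + 0.842)/atanh 0.39)² + 3 = (2.802/0.4118)² + 3 = 49.3, so 50. Power at n = 50 is 80.6%. The figure reproduces. It concerns a correlation between CBF and MD/FA, not a treatment contrast.

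**2. What each quantity estimates.** Let δ be the ACZ effect on 24-week change, taken as equal in both on-drug windows. Let c₁ and c₂ be the natural change over weeks 0–24 and 24–48.

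| Quantity | Expected value |
|---|---|
| Early-start change, weeks 0–24 (ACZ) | δ + c₁ |
| Delayed-start change, weeks 24–48 (ACZ) | δ + c₂ |
| Delayed-start change, weeks 0–24 (placebo; in neither MD/FA window) | c₁ |
| Pooled on-ACZ change, equal arms | δ + (c₁ + c₂)/2 |
| Group term over the stated windows | c₁ − c₂ |
| Randomised week 0–24 contrast | (δ + c₁) − c₁ = δ |

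The pooled change carries the natural change one for one. The group term over the realigned windows contains no δ. Only the last row isolates the drug effect.

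**3. Are the data there?** Stage 3 Visit 1 uses the Stage 2a sequence list, which includes multi-shell diffusion imaging. Visit 5 (week 24) uses the same sequences, and Visits 2 to 4 omit at most the DSC sequence. Both arms therefore have DTI at weeks 0 and 24 under blinded treatment.

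**4. Precision of the randomised contrast.** Assumptions: 50 completers, 1:1 allocation (the ratio is not stated), two-sided 0.05, a simple two-sample comparison of change scores, in SD units of the change.

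- 95% CI half-width = t(48) × √(2/25) = 2.011 × 0.2828 = 0.57 SD.
- Power (noncentral t): 41% at 0.5 SD, 18% at 0.3 SD. Detectable at 80% power: 0.81 SD.
- With baseline adjustment at the plan's within-subject correlation of 0.5, the SD of change equals the outcome SD, since 2(1 − 0.5) = 1. The SD falls by √0.75 = 0.866, giving a half-width of 0.49 SD, 52% power at 0.5 SD and a detectable effect of 0.70 SD.
- The pooled on-ACZ change has half-width t(49)/√50 = 2.010/7.071 = 0.28 SD. It is tighter, but estimates a different quantity.

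These figures describe this contrast under these assumptions. They are not a check of the plan's CBF sample size.

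**5. Hypothetical illustration.** The documents give no natural MD/FA change, so these drifts are invented. With δ = 0 and c₁ = c₂ = 0, 0.1, 0.2 or 0.3 SD, a pooled before–after t test on 50 patients rejects in 5%, 11%, 28% or 55% of trials (exact noncentral t). In simulation the randomised contrast rejects in about 5% throughout. With δ = 0.5 SD in both windows, a group term over the stated windows averages 0 and rejects in about 5%.

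**The case against.** The strongest reply is that the contrast is already implied. Models for all outcomes carry group and group-by-time terms, the MD/FA model inherits the CBF terms, and the Stage 3 text in Summary of Study Design says imaging measures will be compared between treatments. MD and FA are described as repeated measures over time, and nothing says the placebo visits are discarded. This stands in part: the contrast is obtainable if all visits are modelled. A reader might infer that the plan rules out a randomised MD/FA estimate; the documents do not support that. But the general sentence gives no window or contrast, and MD and FA are not in the list before it. The MD/FA model also adds the increased-CBF indicator, a post-randomisation variable on the hypothesised causal path, so a group-by-time coefficient from it need not be the total drug effect.

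Second, the CBF-region comparison answers a stated aim, namely relating DTI change to CBF. That is correct, and natural change common to both kinds of region cancels there; only differential change would remain.

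Third, a reader might take the 11% to 55% rejection rates as this trial's false-positive risk. The documents do not support that either. The drifts are assumed, and the plan never says that a before–after change will be read as a drug effect.

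Fourth, MD/FA is not the whole key secondary endpoint. The point is confined to its DTI component.

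**Conclusion.** The concern holds in a limited form. For MD and FA the plan states windows in which everyone is on ACZ and names only non-randomised comparisons, while the week 0–24 between-arm contrast is named for global CBF alone. The DTI part of the tissue-integrity question therefore gets no specified controlled answer, although the design and scans can provide one. The contrast is unnamed, not impossible.

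The size of any bias cannot be derived from the documents: it equals the natural change, in either direction, and matters only if the on-drug change is interpreted as a drug effect. The precision figures rest on 25 completers per arm and a simple change-score comparison. This is a cheap improvement, not a flaw that invalidates the trial.

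**What to change.** Add to section 11:

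> The treatment effect on MD and on FA is the ACZ-minus-placebo difference in change from week 0 to week 24. It is estimated from a mixed model with treatment group, time, group-by-time, disease duration and a random intercept, fitted to phase 1 visits in both arms, without the post-randomisation increased-CBF (yes/no) term. It is estimated in lesions present at baseline and separately in non-lesional white matter, with regions clustered within patient, and reported with a 95% CI.

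Keep the pooled on-ACZ change, the 15% CBF split and the lesion/non-lesion comparison, labelled descriptive or mechanistic.

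The cost is SAP wording and one further model per measure and tissue set; no patients, visits or scans are added. The drawback is the low precision shown above, so the result should be presented as an estimate with its interval and not as a powered test.

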The primary endpoint of this study will be to determine if therapy with oral divided-dose ACZ administered each day for week-long period results in at least 15% increase in CBF. Studies have shown between 10% - 15% decrease in cerebral perfusion in patients with relapsing MS (Adhya et al., 2006). Therefore, increases in CBF of at least 15% might result in change to lesion evolution. Baseline CBF measures will be compared to measures obtained at each dose escalation step using paired *t* test and Mann-Whitney test.

Determine the effect of long-term oral ACZ on lesion evolution. The key secondary endpoint of this study is to determine if long-term use of oral daily divided-dose with ACZ improves tissue integrity in a proportion of MS lesions.

MRI scans will be segmented using into white and gray matter, T2 and T1 lesion components and contrast-enhancing lesion component. Expert raters (I.V., S.D., L.F.), who are blinded to treatment arm (see section 6.1) will perform quality control of the automated segmentation and obtain quantitative measures of cerebral perfusion. The number and volume of T2 hyperintense and T1 hypointense lesion will be determined using MRIAP. The ratio of T1 hypointense/T2 hyperintense lesion will be determined for baseline and each crossover period and correlated with CBF, CBV and MTT measures obtained at similar times using the Spearman rank correlation.

Diffusion tensor imaging (DTI) is a reliable, validated technique that quantitatively measures molecular diffusivity within tissue and provides information about its microstructural integrity. DTI will be used to monitor tissue integrity and correlate change with increases in CBF following ACZ.

Tertiary Objectives

Several studies have quantitated transverse and longitudinal relaxation times within lesions and normal-appearing white matter and gray matter. These studies have shown that changes in both transverse and longitudinal relaxation can precede lesion formation and possibly better evaluate lesion evolution as compared to black hole volumes (Papadopoulos et al., 2010; van Walderveen et al., 1999a; Walsh et al., 2014; Warntjes et al., 2013). We will manually delineate regions of interest within lesions to obtain T2 and T1 relaxometry metrics. Lesions within areas with greatest change in CBF will be compared with those with least change. We anticipate a correlation between relaxometry measures and areas with varying CBF.

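### The 80% power for the CBF–MD/FA link is stated for a correlation, but the only MD/FA model in section 11 splits regional CBF at 15%

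*Combined protocol and SAP*

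**What the plan says.** Three places bear on this point.

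- **Objectives (Primary & Key Secondary Objective).** On diffusion imaging: "DTI will be used to monitor tissue integrity and correlate change with increases in CBF following ACZ". No cut-point is mentioned, and no method is named for this correlation. The Spearman correlation in that section is for the T1/T2 lesion ratio.
- **Sample Size and Statistical Methods, power.** "With 50 patients, for Aim 1.2", the plan says, "we will have 80% power to detect an average correlation as low as 0.39 between CBF and MD or FA". The label Aim 1.2 is not defined elsewhere in the document.
- **Sample Size and Statistical Methods, secondary outcomes.** MD and FA changes over the 24 weeks on ACZ are analysed by linear mixed model, with repeated measures over regions and times. Then: "These changes will be compared between regions with and without increased CBF (>15% difference from baseline"). And: "Terms in the model will be as for CBF with the addition of increased CBF (yes/no) for the region". No model relating MD or FA to continuous CBF appears in the section.

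For the clinical outcomes, the same section enters changes in CBF, CBV and MTT one at a time as time-varying covariates, with no cut-point.

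**The concern.** The objective and the power statement both describe a correlation, which uses the full size of each CBF change. The specified model uses only whether a region passed 15%, so a region at +16% counts the same as one at +80%. If MD and FA vary roughly in proportion to perfusion, the split discards information, and the stated power belongs to a different analysis.

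At stake is the trial's mechanistic test, whether better perfusion goes with better tissue integrity, in a pilot meant to inform a larger trial. If the yes/no comparison is null, a reader who relies on the 80% statement would give that null more weight than the planned calculation supports.

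**Working it through.** **Inputs.** From Sample Size and Statistical Methods:
- n = 50, r = 0.39, stated power 80%.
- Cut-off 15%.
- Expected effect: "we expect to see a 15% difference between the ACZ treatment and placebo groups".
- SD, given for "improvement in global cerebral perfusion with standard deviation (SD) of 30" per cent. No regional SD is given.

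Assumptions:
- The 0.05 level, stated for the primary outcome, is two-sided and applies here too.
- Changes are normally distributed.
- The 15% group difference is read as the mean gain on ACZ, that is, no mean change on placebo.

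**1. Reproduce the stated power.** Fisher z, continuous CBF, one CBF/diffusion pair per patient: power = Φ(atanh(r)·√(n−3) − 1.96).
- atanh(0.39) = 0.412; √47 = 6.856; product 2.823.
- Φ(2.823 − 1.96) = **80.6%**. A simulation of 40,000 trials gave 81.5%.

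The stated figure is therefore the power of a continuous correlation on 50 independent pairs.

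**2. Apply the split on the same basis.** Under a linear relation, splitting CBF at c = (15 − mean)/SD multiplies the correlation by φ(c)/√(p(1−p)), where p = 1 − Φ(c).

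| Mean gain | c | p | Factor | Correlation | Power (Fisher z) | Power (simulated) |
|---|---|---|---|---|---|---|
| 15% | 0 | 0.50 | 0.798 | 0.311 | 59.7% | 61.4% |
| 0% (SD 30%) | 0.5 | 0.309 | 0.762 | 0.297 | 55.6% | 57.2% |

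The first row is closer to the plan, because the MD/FA analysis covers ACZ periods only (delayed-start patients are re-baselined at week 24). It does not depend on the SD, because the cut falls at the mean. The second row does: 44.1% at SD 15% and 57.9% at SD 45%. In information terms the split keeps 0.762² = 58% to 0.798² = 64%.

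**3. Several regions per patient.** The documents give neither the number of regions nor their correlation, so this step shows direction only. A random-intercept simulation assumed r = 0.39 in every region, equal intraclass correlations of 0.3 to 0.95 for CBF and for the MD/FA residual, and a mean gain of 0 or 15%.
- 2 regions: split 48–89%.
- 4 regions: split 63–99%.
- Continuous CBF in the same settings: 98–100%.

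The split lost power in every case not already at the ceiling, but the level is not fixed.

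**4. Illustration of the cut-off.** If the global SD of 30% applied to each region and were all noise, P(change > 15% | no true change) = 1 − Φ(15/30) = 30.9%. At SD 15% it is 15.9%, and at SD 45% it is 36.9%.

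**The case against.** The strongest defence is that the 15% cut-off is pre-specified and has a reason: the plan ties it to a reported 10–15% perfusion deficit in relapsing MS. Whether regions that regain that deficit do better is a fair threshold question. If the true relation were a step at 15%, the loss would run the other way. At a 50/50 split, a correlation of 0.39 with the yes/no variable becomes 0.39 × 0.798 = 0.311 with continuous CBF, which has about 60% power. This stands as a reason to keep the grouping. It does not make the stated power apply to it, and the plan says only that such an increase might alter lesion evolution, which does not establish a step within single regions.

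Three stronger readings are tempting, and the documents do not support them.

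- *That the planned analysis has 56–61% power.* Those figures hold for one pair per patient. The plan uses several regions and times and speaks of an average correlation.
- *That, by the plan's own SD, about 31% of unaffected regions will be labelled as increased.* The 30% describes improvement in global CBF and may include real differences in response, which would lower the share. Noisier regional measurement would raise it.
- *That the correlation analysis has been dropped.* The objectives still call for it, and the undefined Aim 1.2 may refer to it. Section 11 does not specify it for MD or FA.

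It is also fair to say that noise in CBF weakens a continuous slope too, and that this is a secondary analysis in a pilot. The primary global CBF comparison is unaffected.

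**Conclusion.** The mismatch is real. The 80% belongs to a continuous correlation, and the only MD/FA model in section 11 uses a yes/no term. With a roughly linear relation, normal changes, two-sided 0.05 and one pair per patient, the split takes the correlation from 0.39 to about 0.31 and power from about 80% to about 60% at the expected 15% mean gain. With no mean gain and SD 30%, the figures are about 0.30 and 56–57%.

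Power for the multi-region model as planned cannot be derived from the documents. The 31% in step 4 is an illustration (about 16–37% for SD 15–45%), not a property of the plan. The point warrants a change to the secondary analysis and does not threaten the primary one.

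**What to change.** In the secondary-outcomes paragraph of Sample Size and Statistical Methods:

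1. Make the region's continuous percent change in CBF the main CBF term in the MD/FA mixed model, as a time-varying covariate like the one already planned for clinical outcomes.
2. Keep the 15% grouping as a pre-specified supportive analysis.
3. State that the 80% power for r = 0.39 refers to the continuous analysis, and say what Aim 1.2 is.

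The cost is a few sentences, with no new data, visits or patients. The main result becomes a slope (for example per 10% change in CBF) in place of a contrast between two groups of regions. It assumes rough linearity, which should be checked with a plot. It recovers the loss due to the split, not the attenuation from CBF measurement noise.

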There are regional differences in cerebral perfusion within the normal human brain. Cerebral perfusion is altered in many disease states, including MS. Altered perfusion has been seen in patients with all MS phenotypes and early in relapsing-remitting disease (Helenius et al., 2003; Papadaki et al., 2013, 2012; Wuerfel et al., 2004). Changes in cerebral perfusion both in a given region and lesion area have been previously described in multiple sclerosis (Juurlink, 2013; Wuerfel et al., 2004). Our own work is consistent with others showing that areas within the brain that are most prone to hypoperfusion appear to be those with minimal collateral flow (Adhya et al., 2006; Helenius et al., 2003; Holland et al., 2012; Juurlink, 2013; Narayana et al., 2014; Wuerfel et al., 2004). It is noteworthy that studies, including our own, have shown increased probability of lesion formation within areas corresponding to expected hypoperfused regions (Debernard et al., 2013; Holland et al., 2014). Diminished regional perfusion and increased energy demand has also been suggested to potentiate axonal loss within lesions and contributes to the evolution of potentially irreversible and progressive tissue injury, visualized on serial MRI as persistent black holes (Trapp and Stys, 2009). Indeed, these changes appear to be dynamic and

Protocol Number: HSC-MS-14-0450, Version No 6, April 1, 2019 Page 5

IRB NUMBER: HSC-MS-14-0450 IRB APPROVAL DATE: 06/27/2019 associated with lesion evolution (Wuerfel et al., 2004).

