This study will utilize female and male MS subjects between 18 and 55.

Rationale for Study Design

This study is designed as a prospective trial using a delayed-start design which is anticipated to lead to a larger randomized phase 3 clinical trial. Subjects will be evaluated prior to and after initiation of therapy to quantify the effect of therapy on lesion evolution. These initial pilot studies will determine the magnitude to which ACZ improves MRI measures of cerebral perfusion and alters the evolution of MS plaques. The studies outlined in this proposal will be useful not only in power calculation for the anticipated larger randomized clinical trial but also determine imaging characteristics of responders and non-responders, as it relates to treatment effect and identify the optimum outcome measures, including frequency at which measurements should be obtained.

Many factors contribute to the formation and evolution of lesions in MS (Cotton et al., 2003; Meier and Guttmann, 2006; Narayana et al., 1998). As much as 60% of MS lesions resolve over six months while the remainder show evidence of persistent damage (Sahraian et al., 2010). In stage 2, MS subjects will be treated with oral ACZ for 24 and 48 consecutive weeks to determine if improved cerebral perfusion will result in improved tissue integrity within lesions.

The formation of new MS lesion is best visualized on contrast-enhanced T1-weighted sequences and usually corresponds to new hyperintense area on T2-weighted MRI. To evaluate both existing and newly formed MS lesion, subjects will obtain both contrast-enhanced and non-contrast MRI.

Stage 1a - Increases in cerebral perfusion after IV ACZ has been seen in healthy persons but not in subjects with MS. In addition to physiologic differences in regional cerebral perfusion, subjects with MS might have exaggerated differences secondary to disease-associated damage. This stage will determine the degree of change, temporal kinetics and difference between various regions in cerebral perfusion after IV ACZ in subjects with MS.

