At the end of week 24, patients initially randomized to Treatment B will take 1000 mg extendedrelease ACZ capsules. Similar imaging and clinical evaluations will be performed for the second 24week period. All subjects will discontinue drug at week 48 and obtain a follow-up clinical visit two weeks later. Based upon established pharmacokinetics, the half-life of drug is between 60-75 hours and one would expect insignificant levels within two weeks of discontinuation.

To maintain blinding, patients, evaluating clinicians and MRI analysts will not be informed of treatment assignment or sequence of scans.

We anticipate that sustained increases in regional cerebral perfusion over 6 months will result in improved tissue integrity as measured using diffusion tensor metrics and fewer MS lesions that evolve to persistent black holes.

HYPOTHESIS AND OBJECTIVES

Hypothesis

The underlying hypothesis of this proposal is that long-term therapy with ACZ will improve cerebral perfusion in subjects with MS and this improved perfusion will result in improved tissue integrity in a proportion of MS lesions. To test this hypothesis, subjects will be treated with ACZ, a currently FDA approved agent previously shown in healthy controls to increase cerebral perfusion (Sullivan et al., 1987; Vagal et al., 2009). Subjects will be scanned at various time points (see sections 4 and 6.3) and quantitative MRI metrics will be used to evaluate lesion evolution during and after discontinuation

of treatment.

Primary & Key Secondary Objective

Determine the degree to which divided daily doses of ACZ improves global and regional cerebral perfusion in subjects with MS.

Study subjects will obtain serial MRI scans prior to, during and after therapy (see sections 4 and 6.3). Cerebral blood flow will be measured using an optimized pCASL technique as described by Aslan (Aslan et al., 2010). This will allow us to test the first component of our hypothesis that treatment with ACZ will result in increased regional and/or global perfusion.

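### The MD/FA comparison between regions with and without a CBF rise uses only on-ACZ windows, so it cannot separate perfusion-driven repair from any association that exists without the drug

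*Combined protocol and SAP*

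**What the plan says.** The Hypothesis section states a causal chain: ACZ raises perfusion, and "this improved perfusion will result in improved tissue integrity in a proportion of MS lesions". The objectives make tissue integrity the key secondary endpoint, with DTI as a measure of it.

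Sample Size and Statistical Methods evaluates "changes in MD and FA from baseline (24 weeks for delayed-start) to 24 weeks (48 weeks for delayed-start) after ACZ therapy". Early-start patients therefore contribute weeks 0-24 and delayed-start patients weeks 24-48, and every window is on ACZ. The stated comparison is: "These changes will be compared between regions with and without increased CBF (>15% difference from baseline" (the bracket closes there). On the model it says: "Terms in the model will be as for CBF with the addition of increased CBF (yes/no) for the region". The base model "will include treatment group and time, group-by-time interaction, and disease duration (stratifying variable) as covariates", plus a random patient intercept. In these windows the group term separates only early from delayed start. No term stands for untreated change, lesion age or lesion activity.

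Two background statements bear on this. The General Introduction says of perfusion changes in MS: "Indeed, these changes appear to be dynamic and" (next line) "associated with lesion evolution". Rationale for Study Design says: "As much as 60% of MS lesions resolve over" six months, with persistent damage in the rest.

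**The concern.** The test's null is that regional CBF change and regional MD/FA change are unrelated during ACZ treatment. The hypothesis it serves is that perfusion raised by ACZ improves tissue. These are different statements. A region whose lesion resolves unaided could change in both CBF and MD/FA over 24 weeks. The contrast would then be significant with no drug effect on tissue. In the other direction, if ACZ helps all regions about equally, regions with and without a CBF rise do not differ and the contrast misses the benefit.

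At stake is the trial's evidence on its second causal step. The delayed-start arm's weeks 0-24 would show what happens without ACZ, but this comparison leaves them out.

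**Working it through.** **1. The plan's own figure.** Section 11 gives 80% power at n = 50 for an average correlation of 0.39 between CBF and MD or FA. By Fisher's z, two-sided 5%: n = ((1.960 + 0.842)/atanh(0.39))² + 3 = (2.802/0.4118)² + 3 = 49.3, so 50. Power at n = 50 is 80.6%. The figure reproduces. It concerns detecting an association, whatever its cause. In the same frame, untreated correlations of 0.1, 0.2 and 0.3 would be called significant 11%, 28% and 56% of the time.

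**2. The region contrast when ACZ-driven perfusion has no effect on tissue.**
- From the plan: 50 evaluable patients, mean CBF rise 15%, SD 30%, cut at 15%, alpha 0.05. The 15% and 30% are stated for global CBF and are borrowed here for regions.
- Assumed, because the documents do not give them: untreated within-patient correlation r between regional CBF change and MD/FA change, number of regions, 30% of variance shared within patient, 1:1 allocation, two-sided testing.

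Version A takes each patient's difference in mean MD change between regions above and below the cut and applies a one-sample t test. Version B is a random-intercept model with start group, disease duration and the CBF indicator, which is closer to the plan.

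| r | A, 4 regions | A, 10 regions | B, 5 regions | B, 10 regions | B, 20 regions |
|---|---|---|---|---|---|
| 0 | 5% | 5% | 4.5% | 5.9% | 5.7% |
| 0.1 | 15% | 32% | 19% | 34% | 63% |
| 0.2 | 42% | 84% | 59% | 89% | 99% |
| 0.3 | 77% | 99% | 90% | 99.9% | 100% |

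Over repeated runs the 4-region figures lie at 13-16% for r = 0.1 and 77-80% for r = 0.3. If ACZ also adds regional CBF variance (extra SD 30%, 10 regions, version B), the figures fall to 19%, 56% and 91%.

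**3. The region contrast under a real, even benefit.** With r = 0 and a 0.5-SD improvement in every region, version A rejects about 5% of the time with either 4 or 10 regions.

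**4. The randomised alternative.** Compare patient-mean MD change over weeks 0-24, 25 per arm. With 10 regions the SD of a patient mean is √(0.3 + 0.7/10) = 0.608. A 0.5-SD regional benefit is then 0.5/0.608 = 0.822 SD, the noncentrality is 0.822 × √12.5 = 2.91, and power is 81%. With 4 regions: 0.689, 0.725, 2.56 and 71%. When there is no tissue effect it rejects 3.9% to 6.3% across all simulated settings.

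**5. Are the data there?** Stage 3 Visit 1 uses the Stage 2a sequence list, which includes DTI and pCASL. Visit 5 (week 24) repeats those sequences before delayed-start patients switch. MD, FA and CBF therefore exist at both ends of the placebo window.

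**6. Would a period-by-CBF interaction settle mechanism?** Not reliably. It holds its level (4.5% to about 6%) if ACZ shifts CBF equally everywhere. If ACZ adds regional variance, the on-ACZ slope is diluted. Untreated within-patient CBF variance is 0.7 × 30² = 630, and adding 30² = 900 multiplies the slope by 630/1530 = 0.41. At r = 0.3 with no tissue effect, the continuous interaction then rejects about 58% of the time, in the wrong direction (14% for the dichotomised form). Requiring a steeper slope on ACZ than on placebo would support a true effect of 0.2 SD per 30% CBF only 3% to 27% of the time.

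**The case against.** The plan frames this as association: Aim 1.2 is powered as a correlation, and the trial is a pilot for a larger randomised study. Nowhere does it say that a positive region contrast will be reported as proof of mechanism. As description the comparison is legitimate, and that stands. It does not remove the problem, because the Hypothesis section states a causal step and section 11 gives no other specified test of it.

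Section 11 also applies group-by-time models to all outcomes, and the Stage 3 design summary promises a comparison of imaging measures between treatments. Either could be read as allowing a randomised MD/FA comparison. But the MD/FA paragraph does not specify one, and its windows exclude placebo.

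The untreated correlation may be small. Patients must have had no therapy change for six months, and the units are regions, which need not be lesions. That stands, and is why the result is a range.

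A reader might infer more than the documents support:
- That the protocol says untreated lesion evolution drives perfusion. It says only that the two are associated, and the surrounding argument runs from low perfusion to injury. Association is enough for the problem.
- That nearly all regions will be classed as increased, leaving few to compare. That needs, for example, a 30% rise with SD 15%. With the plan's 15% and 30%, about half of the regions exceed the cut.

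**Conclusion.** The concern holds conditionally. The region comparison is a valid test of association on ACZ, but it cannot attribute that association to ACZ-driven perfusion. If regional CBF and MD/FA changes are correlated without the drug, at an assumed r of 0.1 to 0.3, it is significant about 13-80% of the time with 4 regions and 32-99% with 10, with no perfusion effect on tissue. For a benefit spread evenly across regions its power is about 5%.

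A reader might infer that the test will reject whatever the truth. The documents do not support that. At r = 0 it keeps its 5% level, and they give neither the size nor the sign of r, nor the number of regions. The rates are two-sided, and a correlation in the unfavourable direction would not be read as support. Strictly, they are the power to detect an association that was assumed. The error lies in reading it as a drug mechanism.

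**What to change.** In the MD/FA paragraph of section 11:
1. Add the delayed-start arm's weeks 0-24 on placebo. Make the randomised ACZ versus placebo comparison of MD and FA change over weeks 0-24 the test of whether ACZ improves tissue integrity.
2. Keep the region comparison, and report the same regional CBF-MD/FA association in the placebo window beside it.
3. State that the region result is an association and is not evidence that ACZ-driven perfusion repairs tissue.
4. Do not make the mechanism claim depend on the period-by-CBF interaction, for the reason in step 6 of the working.

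This needs only SAP wording, with no new scans or patients. The randomised comparison rests on about 25 evaluable patients per arm instead of 50 pooled on-ACZ windows, and the wording on mechanism must be more cautious.
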